4.3.1.3 Metabolic Assessments

Metabolic assessments include assessments of hypertension (systolic blood pressure [SBP] and diastolic blood pressure [DBP]), waist circumference, fasting assessments of insulin resistance (hemoglobin A1c [HbA1c], fasting glucose, fasting insulin, and homeostatic model assessment of insulin resistance [HOMA-IR]), assessments of dyslipidemia (total cholesterol, low-density lipoprotein [LDL] cholesterol, high-density lipoprotein [HDL] cholesterol, and triglycerides).

Fasting HOMA-IR, fasting glucose, fasting insulin, total cholesterol, and LDL cholesterol will be assessed as part of clinical laboratory. SBP, DBP, BMI, body weight, and WC will be assessed as part of vital signs.

4.3.1.4 Dual-Energy X-ray Absorptiometry Scan

DXA is a whole-body scan that measures both total body composition (including the mass of fat, bones, and lean tissue) and bone mineral density (BMD) (spine t- and z-scores, hip t- and z-scores,). DXA scans will be performed at Day 1 (baseline), Week 24, Week 52, and Week 76 of the Treatment Period; Week 124, Week 172, Week 220, Week 268, and Week 316 of the optional, Open-Label Extension Period.

4.3.1.5 Testicular Adrenal Rest Tumors

Complete scrotal ultrasounds will be obtained for male subjects to detect and to evaluate the size (volume) and number of TARTs. The initial scrotal ultrasound may be scheduled for any time before the first dose of study drug and will be considered the baseline measurement for the TART assessment. Only subjects with detectable TART(s) at baseline will be followed for TART changes at Week 24, and Week 76 of the Treatment Period; Week 124, Week 172, Week 220, Week 268, and Week 316 of the optional, Open-Label Extension Period.

4.3.1.6 Quality of Life Assessments: Short Form 36

Quality of life will be measured using the SF-36, which will be administered on Day 1 (baseline), Week 24, and Week 76 of the Treatment Period; Week 124, Week 172, Week 220, Week 268, and Week 316 of the optional, Open-Label Extension Period.

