12.6 Exploratory Efficacy Endpoint Analyses

The analysis population for Exploratory Efficacy Endpoint analyses is the ITT analysis set, including all classic CAH subjects who were randomized into the study.

The following Exploratory Efficacy Endpoints will be described in this section:

Table 15 Exploratory Efficacy Endpoints

Objectives	Endpoints	Analysis
Exploratory Efficacy		
To evaluate the percentage change in GC use in subjects with CAH	3.1 Percent change from baseline in GC dose at Week 24	Primary Analysis
To evaluate the effect of tildacerfont in reducing the cumulative HCe dose in subjects with CAH	3.2 Change in total cumulative GC dose in HCe at Week 24	Primary Analysis
To evaluate the effect of tildacerfont in improving HOMA-IR in subjects with CAH	3.3 Change from baseline in the HOMA-IR at Week 24	Primary Analysis
To evaluate the effect of tildacerfont in improving HOMA-IR after 52 weeks of tildacerfont treatment in subjects with CAH	3.4 Change from baseline in HOMA-IR at Week 52	Final Analysis
To evaluate the effect of tildacerfont in reducing cardiovascular risk in subjects with CAH	3.5 Proportion of subjects with improvement in at least one cardiovascular risk factor at Week 52	Final Analysis
To evaluate the effect of tildacerfont in reducing GC use to near-physiologic levels while maintaining androgen control in subjects with CAH	3.6 Proportion of subjects with GC dose \leq 11 mg/m ² /day and A4 \leq 1.2x baseline or \leq ULN at Week 52	Final Analysis
To evaluate the effect of tildacerfont in reducing GC use to near-physiologic levels while maintaining androgen control in subjects with CAH	3.7 Proportion of subjects with baseline GC dose \leq 35mg HCe who achieve GC dose \leq 11 mg/m ² /day in HCe and A4 \leq 1.2x baseline or \leq ULN at Week 52	Final Analysis
To evaluate the effect of tildacerfont in improving quality of life in subjects with CAH	3.8 Change from baseline at Week 24 in the SF-36 domains and composite scores	Primary Analysis
To evaluate the effect of tildacerfont in improving quality of life in subjects with CAH	3.9 Change from baseline at Week 52 in the SF-36 domains and composite scores	Final Analysis
To evaluate the effect of tildacerfont on BMI after 24 weeks in subjects with CAH	3.10 Percent change from baseline in BMI at Week 24	Primary Analysis

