To evaluate the effect of tildacerfont on BMI after 52 weeks of tildacerfont treatment in subjects with CAH	3.11 Percent change from baseline in BMI at Week 52	Final Analysis
To evaluate the effect of tildacerfont on waist circumference after 24 weeks of tildacerfont treatment in subjects with CAH	3.12 Change from baseline in waist circumference at Week 24	Primary Analysis
To evaluate the effect of tildacerfont on waist circumference after 52 weeks of tildacerfont treatment in subjects with CAH	3.13 Change from baseline in waist circumference at Week 52	Final Analysis

Objectives	Endpoints		Analysis
To evaluate the effect of tildacerfont in improving body composition after 24 weeks of tildacerfont treatment in subjects with CAH	3.14	Change from baseline in percent total fat mass and total percent lean mass at Week 24	Primary Analysis
To evaluate the effect of tildacerfont in improving body composition after 52 weeks of tildacerfont treatment in subjects with CAH	3.15	Change from baseline in percent total fat mass and total percent lean mass at Week 52	Final Analysis
To evaluate the effect of tildacerfont in improving BMD after 52 weeks of tildacerfont treatment in subjects with CAH	3.16	Change from baseline in BMD at Week 24 and Week 52	Primary (Week 24) and Final Analysis
To evaluate the effect of tildacerfont in reducing TART(s) in male CAH subjects with TART(s) at baseline after 24 weeks of tildacerfont treatment in subjects with CAH	3.17	Reduction in TART volume at Week 24 in male subjects who had TART(s) at baseline	Primary Analysis
To evaluate the effect of tildacerfont in reducing TART(s) in male CAH subjects with TART(s) at baseline after 52 weeks of tildacerfont treatment in subjects with CAH	3.18	Reduction in TART volume at Week 52 in male subjects who had TART(s) at baseline	Final Analysis
To evaluate the effect of tildacerfont in reducing GC use while maintaining normal A4 levels at Week 24 in subjects with CAH	3.19	Proportion of subjects with at least a 5 mg/day HCe reduction from baseline (Day 1) in GC dose and $A4 \leq 1.2 \times$ baseline or \leq ULN at week 24	Primary Analysis
To evaluate the effect of tildacerfont in reducing GC use while maintaining normal A4 levels at Week 52 in subjects with CAH	3.20	Proportion of subjects with at least a 5 mg/day HCe reduction from baseline (Day 1) in GC dose and $A4 \leq 1.2 \times$ baseline or \leq ULN at week 52	Final Analysis

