12.6.1 Analysis for Change and Percent Change from Baseline at Week 24 Exploratory Efficacy Endpoints 3.1, 3.3, 3.4 and 3.8 to 3.15

A MMRM or ANCOVA model will be used to analyze Exploratory Efficacy Endpoints 3.1, 3.3, 3.4 and 3.8 to 3.15 in the same manner as described in [Section 12.3.3](#); MMRM will be for endpoints with more than one post-baseline assessment, and ANCOVA will be used for endpoints with only one post-baseline assessment at Week 24. The dependent variable will be the absolute or percent change from baseline and the principal treatment effect of interest is at 24 weeks. The LS mean of change from baseline, SE of the LS mean, two-sided 95% CI of the LS mean, LS mean difference of change from baseline between the tildacerfont group and the

placebo (i.e., tildacerfont – placebo), SE of the LS mean difference, and 95% CI of the LS mean difference and its 2-sided p-value will be extracted from the model.

In terms of descriptive statistics, the change from baseline will be reported by treatment group for the reported value and change from baseline value, and percent change from baseline value (if applicable) will be presented by scheduled time point (i.e., Baseline [reported value only] and Week 24).

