12.6.1.2 Subgroup Analyses

Subgroup analyses to Exploratory Efficacy Endpoints 3.1, 3.3, 3.4 and 3.8 to 3.15 will be performed as per [Section 12.5.2](#).

12.6.2 Analysis for Change and Percent Change from Baseline at Week 52 Exploratory Efficacy Endpoints 3.9, 3.11, 3.13, 3.15 and 3.16

An ANCOVA model will be used to analyses Exploratory Endpoints 3.9, 3.11, 3.13, 3.15 and 3.16. The absolute or change or percent change from baseline (placebo-controlled baseline; see section 8.3.9) to 52 weeks will be the dependent variable. The ANCOVA model will include terms for treatment group (0: placebo, 1: tildacerfont); the randomization strata: sex (0: male, 1: female) and baseline GC dose (in HCe, 0: < 40 mg/day, 1: \geq 40 mg/day); and baseline GC type (0: short-acting, 1: intermediate-acting or combination) as categorical explanatory variables. The difference in LSmeans between randomised treatment groups at Week 52 along with the associated CI and 2 sided p-value will be extracted.

Further, a paired t-test will be used to compare the change from tildacerfont-baseline to 52 weeks on treatment with tildacerfont.

In terms of descriptive statistics, for each type of analysis, the change from baseline will be reported by treatment group for the reported value and change from baseline value, and percent change from baseline value (if applicable) will also be presented.

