12.6.3 Exploratory Efficacy Endpoints 3.5 to 3.7 and 3.17 to 3.20, Responder Analyses

Exploratory Efficacy Endpoints 3.5 to 3.7 and 3.17 to 3.20 are responder endpoints and will be analyzed in the same manner as Secondary Efficacy Endpoint 2.1.

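### Exploratory endpoints 3.9 (SF-36) and 3.18 (TART volume) are compared between arms at Week 52, a visit at which neither assessment is scheduled

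*SAP*

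**What the plan says.** **Schedule.** SAP 4.3.1.6 refers to the "SF-36, which will be administered on Day 1 (baseline), Week 24, and Week 76 of the Treatment Period". For ultrasound, SAP 4.3.1.5 states: "Only subjects with detectable TART(s) at baseline will be followed for TART changes at Week 24, and Week 76 of the Treatment Period". The schedules of activities (Protocol 1.3.4, SAP Table 3) show no Week 52 mark for either assessment, although HADS and DXA each have one.

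**Endpoints.** SAP Table 15 defines 3.9 as "Change from baseline at Week 52 in the SF-36 domains and composite scores" and 3.18 as "Reduction in TART volume at Week 52 in male subjects who had TART(s) at baseline". SAP Table 5, SAP 5.1.3.6 and 5.1.3.11, the Protocol synopsis and Protocol Section 3 also use Week 52.

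**Analyses.**
- SAP 12.6.2 fits an ANCOVA to 3.9: "The difference in LSmeans between randomised treatment groups at Week 52 along with the associated CI and 2 sided p-value will be extracted".
- The same section adds a within-subject test: "Further, a paired t-test will be used to compare the change from tildacerfont-baseline to 52 weeks on treatment with tildacerfont".
- SAP 12.6.3 covers 3.18: "Exploratory Efficacy Endpoints 3.5 to 3.7 and 3.17 to 3.20 are responder endpoints and will be analyzed in the same manner" as secondary endpoint 2.1, that is, by logistic regression with an exact score test between arms.
- SAP 12.6.1, which is headed as a Week 24 analysis, also takes in 3.9: "A MMRM or ANCOVA model will be used to analyze Exploratory Efficacy Endpoints 3.1, 3.3, 3.4 and 3.8 to 3.15".

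**The concern.** Two endpoints carry a between-arm test at a visit where nothing is collected for them. If the plan is run as written, the Week 52 contrasts for SF-36 and TART volume rest on whichever few subjects had an early-termination assessment in the window. Otherwise someone has to choose a substitute time point at the Final Analysis, after the Week 24 data have been unblinded. Prespecification is meant to prevent that choice.

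The within-subject SF-36 test has a related gap. Protocol 9.4.1 describes analyses after 52 weeks of tildacerfont as pooling both arms, but only one arm has an SF-36 scheduled at that exposure. Endpoint 3.9 also sits in both the Week 24 section and the Week 52 section of the SAP, so its analysis time point is stated in two ways.

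**Working it through.** The plan states no figure to reproduce. The check is whether any scheduled assessment falls in the Week 52 window, and what exposure each scheduled assessment represents.

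**Inputs.** The Week 52 analysis window is Days 324 to 408 (SAP Table 12). The Week 24 visit is Day 169 and the Week 76 visit is Day 533 (Protocol 1.3.4, SAP Table 3). SAP Table 12 sets the Week 76 target one day later, at Day 534. Planned N is 45 per arm (SAP 6). Placebo subjects start tildacerfont after Week 24.

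**Step 1: distance from the window.**
- Window length: 408 − 324 + 1 = 85 days.
- Week 24 visit to opening: 324 − 169 = 155 days. With six days' lateness the visit is at Day 175, still in the Week 24 window (149 to 197).
- Closing to Week 76 visit: 533 − 408 = 125 days (126 from Day 534). At three days early the visit is at Day 530, still in the Week 76 window, which opens at Day 493.
- Scheduled SF-36 or ultrasound values in Days 324 to 408: 0 in each arm.

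**Step 2: can anything else fill the window?**
- Early-termination visits include both assessments. They come only from subjects who stop early, and Protocol 7.2 expects withdrawal to be uncommon.
- Make-up visits under Protocol 11.2 replace missed in-clinic activities and would reach the window only rarely.
- No rule carries Week 24 or Week 76 values to Week 52. The closest-visit rule in SAP 8.4 works inside the bounded windows of Table 12.
- Imputation is optional for both endpoints (SAP 12.6.2.1, 12.6.3.1). Strategies (a) and (b) in SAP 12.3.3.1 are written for GC dose up to Week 24. The responder model in SAP 12.5.1.2 conditions on response at Weeks 3, 6, 12 and 18, when no ultrasound is scheduled. Neither would have scheduled Week 52 values to learn from.
- If missing counted as failure, as Protocol 9.4.2 says for proportions, nearly every subject would be a non-responder for 3.18 by default.

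**Step 3: weeks on tildacerfont at each visit.**

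| | Week 24 | Week 52 | Week 76 |
|---|---|---|---|
| Tildacerfont-first | 24 | 52 | 76 |
| Placebo-first | 0 | 52 − 24 = 28 | 76 − 24 = 52 |
| SF-36 scheduled | yes | no | yes |

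An SF-36 at 52 weeks on drug is scheduled only for placebo-first subjects, as change from Week 24 to Week 76. That is about 45 of 90 planned, and 45 is a ceiling because the pair requires reaching Week 76. The other 45 or so are scheduled at 24 and 76 weeks on drug, never at 52. The exposure gap between arms is 52 − 28 = 24 weeks at Week 52 and 76 − 52 = 24 weeks at Week 76.

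**The case against.** **Week 52 may mean 52 weeks on drug.** The objective for 3.18 is worded that way. Protocol 9.4.6 defines the period as Week 52 for the tildacerfont group and Week 76 for the placebo group, and SAP 8.3.9.2 supplies a pre-tildacerfont baseline. On that reading placebo-first subjects have a scheduled pair for TART as well as SF-36, and this part stands. It does not rescue the plan, because the tildacerfont group still needs a Week 52 value that is not scheduled. The ANCOVA in SAP 12.6.2 uses the randomisation baseline and so runs on study time. The SAP plans no within-subject TART test, although Protocol 9.1 contains a generic comparison with baseline.

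**Little is lost.** Both endpoints are exploratory and outside the error control in SAP 9.6. Both arms are on tildacerfont by Week 52, and the placebo-controlled contrasts (3.8 and 3.17 at Week 24) are scheduled. This is right and limits the importance of the point. It does not give the Week 52 tests any data.

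**The ultrasound row is ambiguous.** In the text form of the schedule tables its later marks fall under Weeks 64 and 80. This looks like a column shift, since SAP 4.3.1.5 says Week 76. If Week 64 were meant, the distance would be 449 − 408 = 41 days, still outside the window.

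**The Week 24 list has other misplaced endpoints.** Endpoints 3.4, 3.11, 3.13 and 3.15 are also 52-week endpoints listed in SAP 12.6.1. True, but that is a separate defect.

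**Conclusion.** The concern holds: the plan is wrong as written. The randomised Week 52 comparisons for 3.9 and 3.18 have zero scheduled observations in either arm, and nothing in the SAP reliably supplies them. The paired SF-36 test can use scheduled data from one arm only, at most about 45 of 90 subjects. The documents do not say how many males are expected to have TART at baseline, so no denominator can be given for 3.18.

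The conclusion rests on the schedule text in SAP 4.3.1.5 and 4.3.1.6 and the windows in SAP Table 12; for ultrasound it survives the alternative Week 64 reading. Primary and secondary conclusions are unaffected. The point should be corrected before the Final Analysis.

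**What to change.** **Preferred change.** Redefine 3.9 and 3.18 at the Week 76 visit, where both assessments are already scheduled.
- Edit SAP Tables 5 and 15 and SAP 5.1.3.6, 5.1.3.11, 12.6.2 and 12.6.3, and record the change in SAP 14, which is still to be completed. Align the Protocol synopsis and Section 3.
- Remove 3.9 from the Week 24 lists in SAP 12.6.1, 12.6.1.1 and 12.6.1.2.
- Report within-subject SF-36 change by arm: placebo-first, Week 24 to Week 76, labelled 52 weeks on drug; tildacerfont-first, Day 1 to Week 76, labelled 76 weeks on drug.
- State that any Week 76 contrast between arms compares 76 with 52 weeks of active treatment, not drug with placebo.

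**Cost.** Wording only, with no added procedure. The tildacerfont-first arm is assessed at 76 rather than 52 weeks of exposure; the 24-week gap between arms is the same. Editing the Protocol needs an amendment under Protocol 10.12. SAP 3 lets the SAP govern where the two differ on planned analyses, so correcting the SAP is the essential step.

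**Alternative.** Add SF-36 and ultrasound at Week 52, as DXA already has. This keeps the endpoint wording but adds procedures and reaches only subjects who have not yet passed Week 52.

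**To settle at the same time.** SAP 12.6.3 calls 3.18 a responder endpoint, SAP 5.1.3.11 defines it as a change in volume, and SAP Table 9 has no TART responder rule. Moving the visit does not resolve that.

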4.3.2 Safety Assessments

Safety will be assessed by repeated clinical evaluations including adverse events (AEs), serious AEs (SAEs), AEs leading to discontinuation/withdrawal, AEs of special interest (AESIs), vital signs, electrocardiograms (ECGs), and clinical laboratory tests (serum chemistry, hematology, and urinalysis).

4.3.2.1 Adverse Events

Investigators will collect information related to AEs throughout this clinical trial beginning at the signing of the first informed consent form (ICF) through the follow-up visit. Events that have not resolved by the end of the follow-up will be followed through resolution, if possible.

4.3.2.2 Vital Signs

The following vital signs will be assessed after the subject has been sitting for approximately 5 minutes: blood pressure (systolic and diastolic; mmHg); pulse rate (beats per minute); respiration rate (breaths per minute); and body temperature (°C); weight (kg); waist circumference (cm). Vital signs will be obtained at Screening, and at every clinic visit during the Treatment Period and Open-Label Extension Period. Waist circumference is measured at Screening, Day 1 (baseline), Week 24, and Week 52, Week 76 of the Treatment Period, and every clinical visit of the Open-Label Extension Period.

4.3.2.3 Physical Examinations

A full physical examination will be performed during the Screening Visit and at Day 1 (baseline), Week 24, and Week 76. Abbreviated physical examinations occur at Week 6, Week 12, Week 18, Week 32, Week 40, Week 52, Week 64 of the Treatment Period; Week 76, Week 124, Week 172, Week 220, Week 268, and Week 316 of the optional Open-Label Extension Period; and Follow-up visit.

Clinically significant adverse findings from the PE will be recorded on the AE eCRF.

4.3.2.4 Electrocardiograms

All 12-lead ECG assessments will include: heart rate (HR), QRS, QT, and QTc intervals, using Fridericia's formula (QTcF). ECGs will be performed at the following visits: Day 1, Week 12, Week 24, Week 52, Week 76 of the Treatment Period; and Follow-up visit as shown in [Table 3](#).

Clinically significant adverse findings from the ECG will be recorded on the AE eCRF.

4.3.2.5 Clinical Laboratory and Urinalysis

Clinical laboratory assessments include hematology, clinical chemistry, coagulation, lipid panel, thyroid panel, and other hormones. Clinical lab assessments will be performed at all clinic visits.

Urinalysis and fasting assessments (hemoglobin A1c [HbA1c], HOMA-IR, fasting glucose, and fasting insulin) are collected at Day 1 (baseline), Week 24, Week 52, and Week 76 of the Treatment Period.

Clinically significant adverse findings from laboratory or urinalysis assessments will be recorded on the AE eCRF.

4.3.2.6 Psychiatric Evaluations

4.3.2.6.1 Columbia–Suicide Severity Rating Scale (C-SSRS)

The C-SSRS will be used during the study to monitor suicidal ideation and behavior. The Baseline/Screening Version of the C-SSRS, which assesses both lifetime history and history from the last 12 months, will be used at screening to determine subject eligibility. The Since Last Visit Version of the C-SSRS will be used at all subsequent visits specified: Day 1, Week 12, Week 24, Week 52, and Week 76 of the Treatment Period; Week 124, Week 172, Week 220, Week 268, and Week 316 of the optional, Open-Label Extension Period.

[figure not shown]
4.3.2.6.2 Hospital Anxiety and Depression Scale (HADS)

Subject anxiety and depression will be monitored during the study using the HADS, assessed at Day 1, Week 12, Week 24, Week 52, and Week 76 of the Treatment Period.

4.3.3 Pharmacokinetic Measurements

[figure not shown]
Sparse plasma samples will be collected for evaluation of the pharmacokinetics of tildacerfont. A single plasma sample will be collected at approximately 8 am for measurement of tildacerfont concentration at each clinic visit (Week 3, Week 6, Week 12, Week 24, Week 52, Week 64, Week 76, and Follow-up) as indicated in [Table 3](#).

Figure 1 Schema of Study SPR001-204 Study Visits

The 6- or 12-week GC conversion only applies to subjects on dexamethasone at the initial Screening Visit who agree to convert to a non-dexamethasone regimen as determined by their physician.

Figure 2 Schema of Study SPR001-204 Optional Open-Label Extension Period

**Table 1 Study SPR001-204 Protocol Schedule of Events at Screening
(Protocol Version 7.0 March, 2022)**

STUDY VISIT NUMBER	Screening Period	
	1a Optional A4 Screening	1b Screening
	In-Clinic Screening Visit	In-Clinic Screening Visit
STUDY DAY	≤45 days before Day 1	≤45 days before Day 1 ¹
Informed consent	X	X
Inclusion/exclusion criteria		X
Demography		X
Medical history		X
As Prior medications from past year		X
Concomitant medications		X
Prior and current GC regimens ²		X
Vital signs ³ , body weight		X
Height		X
Waist circumference		X
Full physical examination		X
C-SSRS		X
HADS		X
Hepatitis B & C and HIV tests		X ⁴
Urine drug screen		X ⁴

¹ Screening information captured within 45 days of the start of Day 1 in this study (particularly screening information transferred from Spruce Biosciences Study SPR001-203) will be used to determine eligibility and fulfill screening requirements for this study.

² Subjects must be on a stable, supraphysiologic dose of GC replacement (defined as ≥30 mg/day and ≤60 mg/day in HCe) for ≥1 month before the Screening Visit. Information to be collected at screening about a subject's current and historical GC therapy during the past year include the type(s) of GC, the regimen(s), reason(s) that the subject is/was on a particular GC regimen, and any GC stress dosing during the past year.

³ Vital signs consist of systolic and diastolic blood pressure, pulse rate, body temperature, and respiration rate and will be measured after a 5-min rest period.

⁴ These clinic activities of the Screening Visit may be conducted remotely (at the subject's home) if approved by the site's IRB/EC.

STUDY VISIT NUMBER	Screening Period	
	1a Optional A4 Screening	1b Screening
	In-Clinic Screening Visit	In-Clinic Screening Visit
STUDY DAY	≤45 days before Day 1	≤45 days before Day 1 ¹
Serum pregnancy test for FCP		X ⁴
Hormones from blood	X ⁵	X ^{4, 6}
Clinical laboratory ⁷		X ⁴
Urinalysis		X ⁴
HbA1c		X ⁴
12-lead ECG		X ⁴
Report subject's status to site		X ⁴

17-OHP = 17 hydroxyprogesterone; A4 = androstenedione; ACTH = adrenocorticotrophic hormone; ALP = alkaline phosphatase; ALT = alanine aminotransferase; AST = aspartate aminotransferase; C SSRS = Columbia–Suicide Severity Rating Scale; EC = Ethics Committee; ECG = electrocardiogram; eGFR = estimated glomerular filtration rate; FCP = female of childbearing potential; FSH = follicle-stimulating hormone; GC = glucocorticoid; GGT = gamma-glutamyl transferase; HADS = Hospital Anxiety and Depression Scale; HbA1c = hemoglobin A1c; HCe = hydrocortisone equivalents; HIV = human immunodeficiency virus; INR = international normalized ratio; IRB = Institutional Review Board; LH = luteinizing hormone; PT = prothrombin time; PTT = partial thromboplastin time; SHBG = sex hormone–binding globulin

⁵ A4 and 17-OHP will be measured. The blood draw for sample will be obtained at 8 AM ± 1 hour prior to a morning GC dose.

⁶ A4, 17-OHP, ACTH, and testosterone will be measured prior to a morning GC dose.

⁷ Clinical laboratory assessments include hematology, clinical chemistry (including liver function tests such as ALT, AST, ALP, GGT, total and direct bilirubin, and total bile acids), coagulation (PT/INR, and PTT), lipid panel, thyroid panel, LH, FSH, SHBG, renin, aldosterone, inhibin B for males only, and estradiol, prolactin, and progesterone for females only. eGFR for screening will be calculated from blood creatinine measured as part of screening clinical chemistry.

Table 2 Study SPR001-204 Protocol Schedule of Glucocorticoid Conversion Period Activities

	Glucocorticoid Conversion Period ¹					
	1 st 6 weeks				2 nd 6 weeks, if GC dose adjustment necessary	
STUDY VISIT NUMBER	2	3	4	GC dose adjustment	-5	-2
STUDY WEEK	-12	-11	-8		-35	-14
STUDY DAY ²	-84	-77	-56		±3	±3
Visit Window (days)		±3	±3		T	V
Study Visit (V)/ Telephone Contact (T)	V	T	V			
Urine pregnancy test for FCP	X					
Hormones from blood ^{3,4}	X		X			X
Hematology ³			X			X
Clinical chemistry ³	X ⁵		X			X
Renin ³	X		X			X
Vital signs ⁶ , body weight	X		X			X
GC accountability and return of used GC to site	X		X			X
Report subject's status to site	X		X			X
Concomitant medications	X	X	X	X		X
Monitor background GC dosing	X ⁷	X	X	X		X
Determine whether subject requires GC dose adjustment/2 nd 6 weeks OR can proceed to Treatment Period				X		
Background GC accountability			X			X

¹ If a subject fails to meet eligibility criteria or cannot tolerate the non-dexamethasone GC regimen during or at the end of the Glucocorticoid Conversion Period, the investigational site will schedule an abbreviated ET Visit to review AEs and concomitant medications and perform an abbreviated physical examination (preferably in the clinic but also permissible via home visit).

² Study days are numbered relative to Day 1 (Week 0), the first day of the Treatment Period, when the subject will take the first dose of study drug. There is no Day 0 (i.e., study days go directly from Day -1 to Day 1).

³ Samples for these lab assessments will be obtained at 8 AM ± 1 hour, after an overnight fast (nothing to eat since the previous midnight) and before any morning dose of GC medication. On the evenings before scheduled laboratory assessments, subjects should take their evening GC dose before 10 PM.

⁴ A4, 17-OHP, ACTH, testosterone, and background GC levels will be measured.

⁵ Total bile acids will not be included in clinical chemistry at the Week -12 visit.

⁶ Vital signs consist of systolic and diastolic blood pressure, pulse rate, body temperature, and respiration rate and will be measured after a 5-min rest period.

⁷ On the first day of the Glucocorticoid Conversion Period, subjects will discontinue their dexamethasone GC regimen and begin taking a non-dexamethasone GC regimen.

	Glucocorticoid Conversion Period ¹					
	1 st 6 weeks				2 nd 6 weeks, if GC dose adjustment necessary	
STUDY VISIT NUMBER	2	3	4	GC dose adjustment	-5	-2
STUDY WEEK	-12	-11	-8		-35	-14
STUDY DAY ²	-84	-77	-56		±3	±3
Visit Window (days)		±3	±3		T	V
Study Visit (V)/ Telephone Contact (T)	V	T	V			
Dispense HC for stress dosing and perform accountability ⁸	X		X			X
Review study diary/GC adherence ⁹	X	X	X		X	X
Review adverse events	X	X	X		X	X
Physical examination (abbreviated)	X		X			X

17-OHP = 17 hydroxyprogesterone; A4 = androstenedione; ACTH = adrenocorticotrophic hormone; EDC = electronic data capture; ET = early termination; FCP = female of childbearing potential; GC = glucocorticoid; T = telephone contact; V = study visit

⁸ Bottles of HC for stress dosing will be dispensed starting at the beginning of the Glucocorticoid Conversion Period and thereafter as needed to replace opened bottles. Accountability for bottles of HC will be performed at every study visit.

⁹ Subjects will use an electronic study diary to document background GC adherence. Female subjects will also use the study diary to record menstrual information (including start and stop dates of menses).

Table 3 Study SPR001-204 Protocol Schedule of Treatment Period and Follow-up Activities

STUDY VISIT NUMBER	Treatment Period												Follow-up ¹	ET
	Placebo-Controlled Treatment Period						Open-Label Period							
5 Base line	6	7	8	9	10		11	12		13	14	15	16	
STUDY WEEK	0	3	6	12	18	24	27	32	40	46	52	64	76	80
STUDY DAY ²	1	22	43	85	127	169	190	225	281	323	365	449	533	Last dose +30 days
Study Visit (V) / Telephone Contact (T) ³	V	V ⁴	V	V	V	V	T	V	V	T	V	V	V	V
Urine pregnancy test for FCP	X		X	X	X			X	X		X	X	X	X
Hormones from blood ^{5,6}	X		X	X	X			X	X		X	X	X	X
Clinical laboratory ^{5,7}	X	X	X	X	X			X	X		X	X	X	X
Urinalysis ⁵	X					X					X		X	X
HbA1c, fasting glucose and insulin, HOMA-IR ⁵	X					X					X		X	X

¹ Subjects who do not continue to the optional Open-Label Extension Period upon completion of the Treatment Period will enter a 30-day Follow-up Period.

² All study visits and telephone contacts should be performed on the indicated study days. In cases where adherence to the foregoing schedule is not possible, all activities for study visits and telephone contacts must be completed within a +6-day window after the indicated study days. The day of the baseline visit (and first dose of study drug) will be considered Day 1 (Week 0), and all other study days are counted relative to Day 1. There is no Day 0 (ie, study days go directly from Day -1 to Day 1).

³ During scheduled telephone contacts, sites will record any AEs and concomitant medications. After receiving A4 results during the Treatment Period, sites will make telephone contacts to applicable subjects regarding GC dose adjustment (detailed later in this Schedule of Activities). Subjects should be instructed to telephone sites if they have any concerns about their health. Telephone contacts initiated by sites and telephone contacts initiated by subjects should be captured in the EDC system as “unscheduled” telephone contacts.

⁴ This visit for safety assessments may be scheduled for any day of Week 3, for any time of day, at the subject’s convenience. Clinical laboratory can be measured at any time of day for this visit and need not occur before the morning dose of GC.

⁵ Samples for these lab assessments will be obtained at 8 AM ± 1 hour, after an overnight fast (nothing to eat after midnight) and before any morning dose of GC medication. On the evenings before scheduled laboratory assessments, subjects should take their evening GC dose before 10 PM.

⁶ A4, 17-OHP, ACTH, and testosterone will be measured.

⁷ Clinical laboratory assessments include hematology, clinical chemistry (including liver function tests such as ALT, AST, ALP, GGT, total and direct bilirubin, and total bile acids), coagulation (PT/INR, and PTT), lipid panel, thyroid panel, LH, FSH, SHBG, renin, aldosterone, inhibin B for males only, and estradiol, prolactin, and progesterone for females only.

	Treatment Period												Follow-up ¹	ET	
	Placebo-Controlled Treatment Period						Open-Label Period								
STUDY VISIT NUMBER	5 Base line	6	7	8	9	10		11	12		13	14	15	16	
STUDY WEEK	0	3	6	12	18	24	27	32	40	46	52	64	76	80	
STUDY DAY ²	1	22	43	85	127	169	190	225	281	323	365	449	533	Last dose +30 days	
Study Visit (V) / Telephone Contact (T) ³	V	V ⁴	V	V	V	V	T	V	V	T	V	V	V	V	V
BSAP, P1NP, CTX-1, U-NTx, Osteocalcin	X					X					X		X		X
PK ^{5,8}		X	X	X		X					X		X	X	X
Genetic sample ⁹	X														
Vital signs ¹⁰ , body weight	X	X	X	X	X	X		X	X		X	X	X	X	X
Waist circumference	X					X					X		X		X
12-lead ECG	X			X		X					X		X	X	X
HADS	X			X		X					X		X		X
SF-36	X					X							X		X
PGIC						X							X		X
Study treatment accountability and return of used treatment to site	X	X	X	X	X	X		X	X		X	X	X		
Scrotal ultrasound for males	X ¹¹					X ¹²						X ¹²		X ¹²	
DXA scan for body composition and bone mineral density ¹³	X					X					X		X		X

⁸ A single blood sample will be drawn for PK measurement at each specified visit.

⁹ Where local regulations permit and subject to discretionary approval from each site's IRB/EC and to subject consent, a voluntary blood sample may be collected for DNA analysis.

¹⁰ Vital signs consist of systolic and diastolic blood pressure, pulse rate, body temperature, and respiration rate and will be measured after a 5-min rest period.

¹¹ The initial scrotal ultrasound may be scheduled for any time before the first dose of study drug and will be considered the baseline measurement for TART.

¹² Scrotal ultrasounds will only be conducted in subjects who had TART(s) at baseline.

¹³ DXA scans should be performed for all subjects as indicated. The initial DXA scan may be scheduled for any time before the first day of study drug and will be

	Treatment Period												Follow-up ¹	ET	
	Placebo-Controlled Treatment Period						Open-Label Period								
STUDY VISIT NUMBER	5 Base line	6	7	8	9	10		11	12		13	14	15	16	
STUDY WEEK	0	3	6	12	18	24	27	32	40	46	52	64	76	80	
STUDY DAY ²	1	22	43	85	127	169	190	225	281	323	365	449	533	Last dose +30 days	
Study Visit (V) / Telephone Contact (T) ³	V	V ⁴	V	V	V	V	T	V	V	T	V	V	V	V	V
Inclusion/exclusion criteria	X														
Concomitant medications	X	X	X	X	X	X	X	X	X	X	X	X	X	X	X
C-SSRS	X			X		X					X		X		X
CGI-I						X							X		X
Randomization to study drug	X														
Dispense study drug ¹⁴	X		X	X	X		X	X			X	X			
Study drug accountability		X	X	X	X	X		X	X		X	X	X		X
Monitor background GC dosing	X	X	X	X	X	X	X	X	X	X	X	X	X	X	X
GC dose adjustment telephone contacts ¹⁵	X		X	X	X		X	X			X	X			

considered the baseline measurement for the bone mineral density endpoint and body composition assessments. Subjects should not take calcium supplements within the 24 hours before a DXA scan.

¹⁴ Either the subject will pick up study drug in the clinic or study drug will be shipped directly to the subject. Study drug will be taken daily between 6 PM and midnight, with an evening meal. The evening meal should contain <50% fat content. Study drug may be consumed up to 30 minutes after completing the evening meal, if necessary.

¹⁵ During the Treatment Period, sites will make telephone contacts to subjects who are eligible for a GC dose adjustment within 2 weeks after each applicable study visit and based on their A4 level at that visit. Subjects who are not eligible for a GC change will not be telephoned. The site will direct the subject to adjust his/her GC dose by no more than 5 mg/day HCe increments if the subject has not experienced any change in clinical status since the previous study visit. If a subject's GC dose is adjusted, the site will telephone the subject again 7 days after the GC dose adjustment to assess for the occurrence of AEs and the initiation of new concomitant medications. GC reductions may begin at Week 2 (based on the Day 1 A4 measurement) and increases in GC dose may begin based on the A4 measurement at Week 6. GC dose may be reduced to a minimum of 15 mg HCe per day (approximately physiologic replacement level).

	Treatment Period												Follow-up ¹	ET	
	Placebo-Controlled Treatment Period						Open-Label Period								
STUDY VISIT NUMBER	5 Base line	6	7	8	9	10		11	12		13	14	15	16	
STUDY WEEK	0	3	6	12	18	24	27	32	40	46	52	64	76	80	
STUDY DAY ²	1	22	43	85	127	169	190	225	281	323	365	449	533	Last dose +30 days	
Study Visit (V) / Telephone Contact (T) ³	V	V ⁴	V	V	V	V	T	V	V	T	V	V	V	V	V
Dispense HC for stress dosing and perform accountability ¹⁶	X	X	X	X	X	X		X	X		X	X	X	X	X
Review study diary/drug adherence ¹⁷	X	X	X	X	X	X	X	X	X	X	X	X	X	X	X
Review adverse events	X	X	X	X	X	X	X	X	X	X	X	X	X	X	X
Physical examination ¹⁸	X		X	X	X	X		X	X		X	X	X	X	X

¹⁶ Bottles of HC for stress dosing will be dispensed starting at Day 1 and thereafter as needed to replace opened bottles. Accountability for bottles of HC will be performed at every study visit.

¹⁷ Subjects will use an electronic study diary to document study drug and background GC adherence. Female subjects will also use the study diary to record menstrual information (including start and stop dates of menses).

¹⁸ A full physical examination will be conducted at Baseline (Day 1), Week 24, and Week 76. The full physical examination may exclude rectal, genitourinary, and breast exams. An abbreviated physical examination will be conducted at all other visits indicated. If the physical exam is performed at the subject's home, the qualified medical professional will report any changes to the subject's health to the site to determine whether further evaluation is needed via an unscheduled visit.

